10.4.2 Analysis of the Primary Efficacy Endpoint(s)

The primary endpoint will be percentage of patients with sustained virologic response after treatment for HCV after lung transplant.

We expect that 100% of patients who are treated will achieve SVR. SVR will be defined as the absence of detectable HCV RNA Quantitative (PCR) testing 3 months after the completion of the treatment course. Any failure of therapy will be considered significant and will result in the halting of further enrollment until further discussed by the safety monitors and the IRB.

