In this pilot study, we propose utilizing HCV positive donors for HCV negative patients on the waiting list for a lung transplant at NYU Langone. Following transplant we will perform serial surveillance for the transmission of HCV viremia from donor to recipient. **We will start HCV therapy post-transplant once viremia is detected. The rationale for delaying treatment until viremia is detected is to prevent unnecessary treatment in patients who never develop viremia.** The main objective is to determine the safety and efficacy of the strategy of transplantation of lungs from HCV positive donors (with or without evidence of active HCV viremia). To evaluate this clinical objective, we will characterize the incidence of HCV viremia in recipients whose lung donors were HCV positive and for recipients who develop viremia, to characterize the time course of the development of viremia, and subsequent clearance of viremia after

CONFIDENTIAL

CONFIDENTIAL

This material is the property of the NYU School of Medicine and Langone Medical Center. Do not disclose or use except as authorized in writing by the study sponsor
Interventional Template Version: 28 APR 2017

With the exception of the use of HCV therapy and the blood testing to evaluate the viremia and the response to therapy, all the other aspects of management of the lung transplant recipients will follow standard of care practices and protocols for lung transplant recipients at NYU Langone Health.

Willingness to participate in this trial will afford patients quicker access to lung transplantation, and will have the potential to reduce if not eliminate waitlist mortality. In particular, the availability of lungs for transplantation in New York State is among the lowest in the country and the evaluation of HCV donors will increase the opportunities for our waitlisted patients to receive organ offers.

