2.4 Potential Risks & Benefits

2.4.1 Known Potential Risks

Risks of treatment failure: HCV mutation can lead to drug resistance and treatment failure. In patients administered Mavyret, the risk of this was 2% or less. For patients with treatment resistant HCV, rescue therapy with alternative agents can result in cure of up to 100% depending upon the genotype. Guidelines for the treatment of resistant HCV strains are published and updated regularly. [16]

Risks of treatment intolerance: Over multiple clinical trials. The overall rate of medication related adverse events leading to permanent discontinuation prior to completion of an 8-week course of therapy was 0.1% [17].

Risk of acute hepatitis C infection: Acute hepatitis C is asymptomatic in 66-75% of patients. The risks of acute HCV leading to fulminant hepatic failure are believed to be very low, however case reports of this do exist [18]. To minimize this already very low risk, we are starting treatment in all the patients at the time of transplant before any viremia is even detected.

Risk of chronic hepatitis C infection: Patients who prove refractory to all therapy including rescue therapy and develop persistent viremia are at risk to develop chronic HCV infection, which has the potential to cause cirrhosis/end-stage liver disease, the potential for the need for liver transplantation and/or death. We expect our treatment failure rate in this study to be 0%, therefore we expect the risk of chronic HCV infection to be 0%. In the event of a treatment failure, the risks of developing chronic HCV must be considered. It is estimated that approximately 15-30% of patients with chronic HCV develop cirrhosis/end-stage liver disease over 20-30 years. [19]. This risk should be compared to the risk of death on the lung transplant waiting list. The reported one-year mortality for a waitlisted patient without a transplant is as high 26.7% [20].

The efficacy of HCV treatment with Mavyret is high (98%). The efficacy of rescue therapies approaches 100%. Even in the event of a treatment failure, the risk of cirrhosis and liver disease secondary to chronic HCV are low. We believe that the survival benefit of receiving an earlier lung transplant, by accepting an organ from a HCV-positive donor, far outweighs the risks of HCV exposure and possible treatment failure.

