6.1.8 Duration of Therapy

The duration of therapy will be 8-weeks.

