- Pregnant Partner Contact Card
- Sample Willingness to Participate Form
- Sample Fact Sheet
- SOP for specimen handling
- Accreditation for the Transplant Laboratory
- Specimen collection and shipping instructions for Quest Laboratories

CONFIDENTIAL

19 Schedule of Events: Surveillance post-transplant with an 8 weeks MAVYRET treatment phase included

Activity	Screening visit (POD-365 to -1)	SURVEILLANCE PHASE					
		POD0	POW1 (+/- 2 day)	POW2 (+/- 3 days)	POW3 (+/- 3 days)	POW4 (+/- 5 days)	POW5 (+/- 5 days)
Study team procedures							
Acknowledgement of willingness to participate and provision of fact sheet	X						
Medical History		X					
Physical Exam		X					
Height		X					
Weight		X					
Vitals signs		X					
Review all donor and recipient inclusion/exclusion criteria		X					
Signing of informed consent		X					
Study specific interventions							
Lung transplant operation		X					
Mavyret treatment (Start and follow up)		X ¹					
Study specific laboratory tests							
Donor serum HCV genotyping		X					
Recipient serum HCV genotyping		Any time during the study (x1) once there is documentation of positive HCV RNA Quantitative (PCR)					
HCV RNA Quantitative (PCR)	X	X ²	X	X	X	X	X
HCV serology (HCV Ab)	X	X ²	X	X	X	X	X

X¹ Mavyret will be initiated post lung transplantation once a viral load is detected

X² If screening lab(s) specifically HCV RNA Quantitative (PCR) and HCV serology (HCV Ab) are performed 14 days or less prior to POD 0, those labs will not be repeated at the POD 0 timepoint.

CONFIDENTIAL

This material is the property of the NYU School of Medicine and Langone Medical Center. Do not disclose or use except as authorized in writing by the study sponsor
Interventional Template Version: 28 APR 2017

Activity	SURVEILLANCE PHASE			POW9 (+/- 5 days)	POW10 (+/- 5 days)	POW11 (+/- 5 days)
	POW6 (+/- 5 days)	POW7 (+/- 5 days)	POW8 (+/- 5 days)			
Study team procedures						
Study specific interventions						
Mavyret treatment (Start and follow up)	X ¹					
Study specific laboratory tests						
Recipient serum HCV genotyping	Any time during the study (x1) once there is documentation of positive HCV RNA Quantitative (PCR)					
HCV RNA Quantitative (PCR)	X	X	X	X	X	X
HCV serology (HCV Ab)	X	X	X	X	X	X

Activity	POW12 (+/- 5 days)	POW 24 - Interim assessment visit (+/- 14 days)	POW 52 - Final assessment visit (+/- 14 days)
Study team procedures			
Mavyret treatment (Start and follow up)	X ¹		
Medical History			X
Physical Exam			X
Height			X
Weight			X

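### SVR is defined 3 months after treatment, but Section 19 times every HCV RNA sample from transplant, so for later Mavyret starts the first qualifying sample in that table is POW52

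*Combined protocol and SAP*

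**What the plan says.** Section 10.4.2 states: "SVR will be defined as the absence of detectable HCV RNA Quantitative (PCR) testing 3 months after the completion of the treatment course". It does not convert 3 months to weeks and gives no window. It adds: "Any failure of therapy will be considered significant and will result in the halting of further enrollment". Section 8.6 also calls an emergency meeting of the DSMB and study team after any treatment failure.

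Section 6.1.8 sets the course length: "The duration of therapy will be 8-weeks". On the start, Section 2.1 says "We will start HCV therapy post-transplant once viremia is detected", and the footnote in Section 19 agrees: "Mavyret will be initiated post lung transplantation once a viral load is detected". Section 2.4.1 says something different: "we are starting treatment in all the patients at the time of transplant before any viremia is even detected". Section 5.5 equates a 12-month minimum participation with 10 months of follow-up after Mavyret.

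Section 19 (Schedule of Events) places HCV RNA at screening, POD0 and every week from POW1 to POW12. Two further columns follow, "POW 24 - Interim assessment visit (+/- 14 days" and "POW 52 - Final assessment visit (+/- 14 days". No column is tied to the end of treatment, and nothing lies between POW24 and POW52. Section 10.4.3 likewise counts its minimum of 6 months of serial testing from transplant.

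**The concern.** The endpoint is timed from the end of treatment and the samples from surgery. The two coincide only if treatment starts within a narrow range of dates. A patient whose viremia appears some weeks after transplant will have been off treatment for less than 3 months at POW24, and the table then offers nothing until POW52.

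Two things are at stake. First, that patient's primary-endpoint value comes late, and it is lost if the patient dies or leaves before POW52. Section 10.5 speaks both of about 70% of 20 patients being treated (14) and of 7, so one missing value is 1/14 = 7% or 1/7 = 14% of the treated group. Second, a relapse after POW24 has no scheduled PCR until POW52. That could delay the enrollment halt in Section 10.4.2 and the emergency meeting in Section 8.6, both of which a treatment failure triggers.

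**Working it through.** **Inputs.** Course length 8 weeks (Section 6.1.8). SVR at 3 months after treatment (Section 10.4.2), read as 12 or 13 weeks because the plan gives no figure in weeks. POW24 window: weeks 22 to 26. POW52 window: weeks 50 to 54 (Section 19). Let s be the week of the first dose. I assume this is the nominal week of the positive sample; each week of delay moves the cut-offs, counted from detection, one week earlier.

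**The plan's own figure.** Follow-up after treatment to week 52 is 52 − (s + 8) weeks. At s = 0 this is 44 weeks, or 10.1 months, which reproduces the 10 months in Section 5.5. At s = 4 it is 9.2 months and at s = 12 it is 7.4 months. The stated 10 months therefore fits only a start at or near transplant.

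**SVR due date.** s + 8 + 12 = s + 20, or s + 8 + 13 = s + 21.

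**Latest start that POW24 can serve.**
- Nominal date: 24 − 20 = POW4, or 24 − 21 = POW3.
- Last permitted day: 26 − 20 = POW6, or 26 − 21 = POW5.
- First permitted day: 22 − 20 = POW2, or 22 − 21 = POW1.

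**Latest start that POW52 can serve.**
- Nominal date: 52 − 20 = POW32, or 52 − 21 = POW31.
- Last permitted day: 54 − 20 = POW34, or 54 − 21 = POW33.

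| Start | Treatment ends | SVR due (12 / 13 weeks) | POW24: weeks after treatment, nominal (window) | POW52: weeks after treatment, nominal |
|---|---|---|---|---|
| Transplant | 8 | 20 / 21 | 16 (14–18) | 44 |
| POW4 | 12 | 24 / 25 | 12 (10–14) | 40 |
| POW6 | 14 | 26 / 27 | 10 (8–12) | 38 |
| POW7 | 15 | 27 / 28 | 9 (7–11) | 37 |
| POW12 | 20 | 32 / 33 | 4 (2–6) | 32 |
| POW24 | 32 | 44 / 45 | not applicable | 20 |

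**Lateness at POW52.** With 12 weeks, starts at POW7 to POW12 are sampled 52 − 27 = 25 to 52 − 32 = 20 weeks after the due date. With 13 weeks, starts at POW6 to POW12 are sampled 52 − 27 = 25 to 52 − 33 = 19 weeks after it.

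**Gap between the last two samples.** 52 − 24 = 28 weeks nominally, and 50 − 26 = 24 to 54 − 22 = 32 weeks with the windows.

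**The case against.** The strongest objection is that the deciding text may exist. The contents list Section 7.3 (study schedule), including intermediate visits, but its text is not in the copy reviewed. The Protocol Summary names surveillance for SVR after treatment as a procedure of its own. A visit timed from the last dose could be in Section 7.3. This stands: a reader might infer that the plan has no 3-month sample at all, and the documents do not support that. Only Section 19 can be faulted.

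Second, the affected group may be empty. The 10 months in Section 5.5 fits starts near transplant, and if everyone starts at transplant, as Section 2.4.1 says, POW24 falls 14 to 18 weeks after treatment and the gap does not arise. This also stands as a limit. It does not remove the point, because Sections 2.1 and 19 say treatment starts on detection, and Section 19 keeps looking for viremia weekly to POW12.

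Third, a reader might infer that late starters have no primary endpoint. That goes too far. Starts up to about POW33 or POW34 still have a qualifying sample at POW52. POW24 is off treatment for every start up to POW12 (12 + 8 = 20, before week 22), so failures present by then are seen, and an unscheduled test could find a later relapse sooner.

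Fourth, some tolerance before 3 months would extend what POW24 covers. With a margin of 2 weeks on the 12-week reading it would serve starts to POW8 (26 − 8 − 10). But Section 10.4.2 states no margin, so none can be assumed.

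Finally, few failures are expected. At the plan's 98% efficacy, 7 to 14 treated patients give 0.14 to 0.28 failures of any kind. A reader might infer that many enrollments would go ahead that should have been halted. The documents give neither the accrual pattern nor the timing of viremia, so no such number can be supported.

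**Conclusion.** The mismatch is real within Section 19. If treatment starts on detection, POW24 meets the plan's SVR definition on its nominal date only for starts up to POW4 (12 weeks) or POW3 (13 weeks), and at best for starts up to POW6 or POW5. Later starts wait for POW52, nominally 32 to 37 weeks after treatment for POW7 to POW12 starts. Starts after about POW34 or POW33 have no qualifying sample.

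The consequence is a late SVR value, at risk of loss, and possibly late detection of a relapse after POW24. It is not a wholly unmeasured endpoint. The conclusion rests on the start rule in Sections 2.1 and 19, on prompt dosing after a positive sample, and on Section 7.3 holding no visit timed from treatment. The plan gives no distribution of time to viremia, so the number affected cannot be computed and may be zero. This should be fixed; my confidence is moderate because Section 7.3 could not be read.

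**What to change.** Add to Section 19 one HCV RNA sample per treated patient, timed from the last Mavyret dose at the plan's own 3 months, stated in weeks and with a window. Let POW24 serve as that sample when it falls in the window. If Section 7.3 already contains such a visit, carry it into Section 19. Put the same weeks and window in Section 10.4.2, and say there whether a later sample such as POW52 may be used when the 3-month one is missing.

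The cost is a schedule amendment, a short addition to Section 10.4.2, and at most one extra or re-timed PCR per treated patient: 7 to 14 on the figures in Section 10.5, and no more than 20. Section 7.2.3 allows outpatient samples to be processed at local laboratories, and Section 14.5 already has the Transplant Institute paying for study PCR.

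Separately, Sections 2.4.1 and 5.5 must be reconciled with Section 2.1 and the Section 19 footnote on when treatment starts. This review takes no position on which is right.

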10.4.3 Analysis of the Secondary Endpoint(s)

Secondary endpoint #1: 1-year patient survival rates in HCV negative lung recipients who receive a lung transplant from a HCV positive donor.

Patients will have regular follow-up as standard of care for all lung transplant recipients. Patients survival will be readily apparent. Furthermore, all deaths of transplant recipients are required to be reported to UNOS.

Secondary endpoint #2: Incidence of HCV viremia among HCV negative recipients who receive a lung transplant from a HCV positive donor.

CONFIDENTIAL

We will be measuring serial HCV RNA Quantitative (PCR) and serologic testing for a minimum of 6-months post-transplant. A patient will be considered to be viremic when a post-transplant HCV RNA Quantitative (PCR) test is positive. The incidence of viremia will be calculated as a percentage of the patients transplanted with a HCV-positive donor who develop HCV viremia by RNA Quantitative (PCR) testing.

10.4.4 Adherence and Retention Analyses

Adherence to the protocol will be assessed by the study team in direct conversations with the patients during routing visits, and will be assessed clinically by evaluation of HCV viral loads.

Clearance of HCV will demonstrate adherence to the regimen. Failure to clear viremia will prompt more detailed direct patient inquiries regarding and will prompt an evaluation of possible treatment resistant strains of HCV as described elsewhere. A rescue course of therapy will be initiated under the direct guidance of a hepatologist and/or transplant infectious diseases specialist.

10.4.5 Baseline Descriptive Statistics

In this study, no designed comparison groups will exist.

10.4.6 Planned Interim Analysis

Interim analysis not applicable

10.4.6.1 Safety Review

Any patient death will result in halting of any further enrollment in the study and an assessment of

whether the death was related to HCV exposure, infection, or treatment. Even in the event of a patient death, currently enrolled patients who are actively being treated for HCV viremia and tolerating therapy will continue to receive therapy so as not to put them at risk for HCV infection and/or the development of resistance as a consequence of interrupted therapy. If the patient death is deemed related to a specific treatment agent, enrolled patients receiving that same agent will be switched to an alternative therapy.

For any patient who is found to experience a treatment, a formal Hepatology consultation will be obtained promptly, and rescue therapy with alternative agents will be initiated under Hepatology guidance.

10.4.7 Multiple Comparison/Multiplicity

Not applicable.

10.4.8 Tabulation of Individual Response Data

Since this is a relatively small trial, individual participant data, in particular as pertains to the kinetics of the development and clearance of HCV viremia, will be evaluated.

10.5 Sample Size

20 patients are expected to enroll in this trial.

We expect that less approximately 70% of patients will develop evidence of HCV infection transmitted from the HCV-positive donor and will be treated for HCV infection. We expect that 100% of the patients who are treated for HCV viremia will achieve SVR.

This is a single-arm study with no comparison group. The power to detect a difference in observed versus expected depends upon the true efficacy of the therapy. The reported efficacy of the therapy is 98%.

With an estimated 7 patients who will be treated, a single treatment failure will be regarded as a significant deviation from the expected outcome.

CONFIDENTIAL

11 Source Documents and Access to Source Data/Documents

Source data is all information, original records of clinical findings, observations, or other activities in a clinical trial necessary for the reconstruction and evaluation of the trial. Source data are contained in source documents. Examples of these original documents, and data records include: hospital records, clinical and office charts, laboratory notes, memoranda, subjects' diaries or evaluation checklists, pharmacy dispensing records, recorded data from automated instruments, copies or transcriptions certified after verification as being accurate and complete, microfiches, photographic negatives, microfilm or magnetic media, x-rays, subject files, and records kept at the pharmacy, at the laboratories, and at medico-technical departments involved in the clinical trial. It is acceptable to use CRFs as source documents.

If this is the case, it should be stated in this section what data will be collected on CRFs and what data will be collected from other sources.

The study case report form (CRF) is the primary data collection instrument for the study. All data requested on the CRF must be recorded. All missing data must be explained. If a space on the CRF is left blank because the procedure was not done or the question was not asked, write "N/D". If the item is not applicable to the individual case, write "N/A". All entries should be printed legibly in black ink. If any entry error has been made, to correct such an error, draw a single straight line through the incorrect entry and enter the correct data above it. All such changes must be initialed and dated. **DO NOT ERASE OR WHITE OUT ERRORS.** For clarification of illegible or uncertain entries, print the clarification above the item, then initial and date it.

Access to study records will be limited to IRB-approved members of the study team. The investigator will permit study-related monitoring, audits, and inspections by the IRB/EC, the sponsor, government regulatory bodies, and University compliance and quality assurance groups of all study related documents (e.g. source documents, regulatory documents, data collection instruments, study data etc.). The investigator will ensure the capability for inspections of applicable study-related facilities (e.g.

pharmacy, diagnostic laboratory, etc.).

Participation as an investigator in this study implies acceptance of potential inspection by government regulatory authorities and applicable University compliance and quality assurance offices.

12 Quality Assurance and Quality Control

QC procedures will be implemented beginning with the data entry system and data QC checks that will be run on the database will be generated. Any missing data or data anomalies will be communicated to the site(s) for clarification/resolution.

Following written SOPs, the monitors will verify that the clinical trial is conducted and data are generated, documented (recorded), and reported in compliance with the protocol, GCP, and the applicable regulatory requirements (e.g., Good Laboratory Practices (GLP), Good Manufacturing Practices (GMP)).

The investigational site will provide direct access to all trial related sites, source data/documents, and reports for the purpose of monitoring and auditing by the sponsor, and inspection by local and regulatory authorities.

CONFIDENTIAL

13 Ethics/Protection of Human Subjects

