2.1 Background Information and Relevant Literature

In New York State, 882 patients have received lung transplants since the year 2000. In that time, however 439 patients either died on the waiting list or became too sick for transplant [1]. Thus, for every 2 patients waitlisted in New York, one patient will die or become too sick for transplant before an organ becomes available. The shortage of organs available for lung transplantation directly results in loss of life.

At the same time, since 2000, in New York alone, thousands of donor organs available for transplantation were discarded because of donor history of HCV infection or exposure [2]. With the availability of new and well-tolerated direct-acting antiviral agents, cure rates for chronic HCV infection approach 100% [3]. Treatment of HCV naïve transplant recipients who develop donor-derived HCV infection post-transplant would be expected to be equally successful. Thus, if post-transplant antiviral treatment could enable HCV positive lung donors to be utilized for negative recipients, then the current donor pool has the potential to eliminate waitlist mortality.

There is, in fact, precedent for this as a viable strategy to narrow the gap between organ supply and demand. A recently study in which HCV positive donor kidneys were transplanted into HCV negative recipients demonstrated both excellent outcomes in terms of allograft function, and 100% HCV cure rates among the recipients [4]. Other ongoing and unpublished series of kidney transplant recipients [5] and of heart transplant recipients [6] have observed that only about 70% of HCV negative recipients who receive an organ from a HCV positive donor actually develop HCV viremia post-transplant. This is not surprising since the designation for HCV donor positivity by UNOS is a positive test for *either* anti-HCV antibody *or* HCV RNA. Donors who test positive for HCV antibody alone may have a falsely positive test, or may have had a prior exposure to HCV with subsequent virus clearance; in either scenario, there would be no risk of transmission of HCV infection to a recipient. It is estimated that one-third of donors designated as HCV positive is, in fact, non-viremic [7].

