5.6 Total Number of Participants and Sites

Twenty patients are expected to be enrolled and transplanted. No sites outside of NYULMC will enroll patients.

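### Section 10.5 expects 7 treated patients, but its own inputs (20 patients, about 70% infected and treated) give about 14, which nearly doubles the chance of at least one failure at 98% efficacy

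*Combined protocol and SAP*

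**What the plan says.** Section 10.5 gives the enrolment ("20 patients are expected to enroll in this trial") and the share to be treated ("We expect that less approximately 70% of patients will develop evidence of HCV infection transmitted from the HCV-positive donor and will be treated"). It states the expected result ("We expect that 100% of the patients who are treated for HCV viremia will achieve SVR"), then remarks on power for observed against expected results and cites a reported efficacy of 98%. It ends: "With an estimated 7 patients who will be treated, a single treatment failure will be regarded as a significant deviation from the expected outcome".

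Other sections support the two inputs. Section 5.6 says "Twenty patients are expected to be enrolled and transplanted", so no loss between enrolment and transplant is planned. Section 2.1 reports from other transplant series that "only about 70% of HCV negative recipients who receive an organ from a HCV positive donor actually develop HCV viremia post-transplant", and adds: "It is estimated that one-third of donors designated as HCV positive is, in fact, non-viremic".

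Section 10.4.2 makes any failure of therapy a reason to halt further enrolment pending discussion. Section 10.4.1 separately plans a comparison of observed with expected failure rates by a two-tailed t-test at p < 0.05.

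**The concern.** Seven is half of what the section's own figures imply. The primary endpoint in 4.2.1 is the percentage of treated patients reaching SVR, so the number treated is its denominator and sets its precision. It also sets how likely a single failure is when the drug performs as reported. An IRB or DSMB member who relies on 7 would put that chance at about half of what the stated inputs imply, and might take one failure as stronger evidence against the treatment than it is.

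There is a smaller matter of wording. The sentence calls one failure a *significant* deviation directly after 98% efficacy and power are mentioned. A reader could take that as a statistical statement against 98%.

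**Working it through.** **Inputs.** N = 20 (10.5; 5.6). Share treated about 0.70 (10.5; 2.1). Alternative share 1 − 1/3 = 2/3, if transmission follows donor viremia (2.1). Reported efficacy 0.98, so failure rate 0.02 (10.5).

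**1. Trying to reproduce 7.**
- 20 × 0.70 = 14.0
- 20 × 2/3 = 13.3
- Applying a 70% reduction twice: 20 × 0.70 × 0.70 = 9.8
- Combining both shares: 20 × 0.70 × 2/3 = 9.3

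None gives 7. Working backwards, 7/20 = 35% treated and 7/0.70 = 10 patients; the plan states neither. The expected number *not* treated comes close (20 × 0.30 = 6; 20 × 1/3 = 6.7), so a slip between treated and untreated is possible, but that is conjecture.

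**2. Chance of at least one failure at 98% efficacy**, 1 − 0.98^n, assuming independent outcomes:
- n = 7: 1 − 0.98^7 = 0.132
- n = 14: 1 − 0.98^14 = 0.246

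This is the chance that the condition in 10.4.2 is met at some point. A failure recognised after enrolment has closed would halt nothing, so the chance of an actual halt is no higher than this.

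**3. Is one failure statistically significant against 98%?** The exact binomial p-value for one failure against a 2% rate is P(X ≥ 1). The two-sided value is the same, because zero failures is more probable than one. It is 0.132 at n = 7 and 0.246 at n = 14. Neither is below 0.05.

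**4. Precision of the SVR percentage** (exact Clopper-Pearson 95% intervals):

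| Treated | No failure | One failure |
|---|---|---|
| 7 | 59.0–100% | 42.1–99.6% |
| 14 | 76.8–100% | 66.1–99.8% |

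Each interval contains 98%, including those with one failure.

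**The case against.** **The 70% may be a ceiling.** The sentence giving it is garbled. If it was meant as less than about 70%, then 14 is an upper limit and 7 is allowed. This stands, and it means that 7 cannot be called strictly impossible. But nothing in the plan gives a rate near 35%, and 2.1 supports about 70% or two-thirds, so the figure remains without a basis.

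**Little depends on 7.** This also stands. No analysis uses it, and the 20 patients are not derived from it. The halt in 10.4.2 and the emergency DSMB meeting in 8.6 apply at any number treated. A reader might infer that the sample size itself is undermined; the documents do not support that.

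**The meaning of *significant* is given elsewhere.** A reader might infer that neither the expectation nor the sense of the word is defined. That goes too far. Sections 4.2.1, 10.2, 10.4.2 and 10.5 all expect every treated patient to respond, and 2.4.1 expects a failure rate of 0%. Section 10.4.2 ties the word to a halt of enrolment. What remains is a small ambiguity from the 98% and power remarks in 10.5 and the test in 10.4.1.

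**The result at n = 7 might seem to turn on the test chosen.** An uncorrected score z-test gives p = 0.020. A pooled two-sample t-test gives 0.022 against an assumed 46 failures in 2300 patients. The plan does not name the first. The second needs a comparator that 2.2.2 does not supply, since the 98% there is not tied to all of the more than 2300 trial patients, and 10.4.5 says there are no comparison groups. Both are poor approximations at this size, so the point should not rest on them.

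**Conclusion.** The expected number treated in 10.5 does not follow from its inputs: 7 is stated, and about 14 follows (13.3 on the one-third figure). The consequence is limited but real. The chance of at least one failure at 98% efficacy is 24.6% rather than 13.2%, and one failure among 14 is compatible with 98%. These figures assume that 98% carries over to this population and that outcomes are independent.

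The number also depends on who is treated. Parts of the Protocol Summary and 2.4.1 speak of treating all patients. The Brief Summary, 2.1, 10.5 and the Schedule of Events speak of treating those in whom viremia is detected. A reader might look to that conflict to explain 7, but it does not: treating all would give 20, and treating on viremia about 14. It is a separate matter, and this point takes no position on which rule is right.

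This is a low-end should-fix. The arithmetic is firm and the effect is on interpretation.

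**What to change.** In 10.5:
- Correct the garbled 70% statement, and restate the expected number treated as about 14 of 20 or give the basis for 7.
- Add the consequence, for example: *If efficacy is 98%, the probability of at least one failure among 14 treated patients is 24.6%. The exact 95% confidence interval for SVR is 76.8–100% if 14 of 14 respond and 66.1–99.8% if 13 of 14 respond, so one failure among 14 is compatible with 98%.* This goes beyond correcting the error, but it is purely descriptive and so fits the approach in 10.4.
- Add one clause saying that the one-failure rule is the enrolment-halt trigger of 10.4.2, measured against the expected 100% SVR, and is not a statistically significant departure from 98%. Whether to keep the halt is for the sponsor.

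As a cross-reference only, note that the passages on who is treated must be reconciled, because the expected number depends on them.

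The cost is a few sentences in 10.5 and IRB approval of the amendment under 13.2. Enrolment, endpoints and data collection do not change. Reconciling who is treated is a larger task and should be handled as its own point.
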